**Table 2: Subperiod definition for AEs** 

EFG = efgartigimod (administration)

With 23:59 added as time part

P Repeat until the last subperiod

The end date/time of the last subperiod will correspond with the end date/time of the last phase as defined in Table 1. AEs starting during the roll-over phase will also be considered as post-TEAEs.

## 2.2.2 Relative day

Relative day in the study (ADY) will be calculated according to the following rule:

- Concerned date < reference date: DY = concerned date reference date
- Concerned date ≥ reference date: DY = concerned date reference date + 1

The reference date is the date of the roll-over visit.

Additionally, relative day in the phase (ADYP) will be calculated using the first day of the phase as reference date.

Relative day in the treatment subperiods (AWADY) will be calculated in the same way, as needed, but using the first day of the subperiod as reference date.

#### 2.2.3 Baseline and change from baseline

The baseline value for 1905 will be the value at the Roll-over visit (which corresponds with the last available value of the 1904 study (at the 1904 EoS visit/1905 Roll-over visit)).

Additionally, for PDAI and PD, changes from 1904 baseline will be presented, with 1904 baseline defined as the last available and non-missing value prior to first IMP administration in the 1904 study (detailed definition of 1904 baseline in 1904 SAP).

SGS	Statistical Analysis Plan	
ARGX-113-1905	Final analysis	Final 1.0 of 26APR2024

Change from baseline at time point t is defined as:

value at time point t – baseline value

Percentage change from baseline at time point t is defined as:

100\*([value at time point t – baseline value] / baseline value)

Furthermore, for PDAI, PD, albumin and LDL-C a treatment period-specific baseline (TPnB) will be defined as the last available and non-missing value prior to the first administration of EFG PH20 SC in treatment period n, with n=1, 2, 3, etc....

Assessments on day 1 of a treatment period without time collection or with time information exactly equal to the time of first IMP administration and which are planned predose will be considered as predose.

Change from TPnB at time point t =

value at time point t – TPnB value.

Percent change from TPnB at time point t =

100\*([actual value at time point t - TPnB value]/ TPnB value).

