# **DEFINITION OF TERMS**

Case report form (CRF)	A printed, optical, or electronic document designed to record protocol required information to be reported to the sponsor for each study participant.
Complete clinical remission (CR)	The absence of new lesions and complete healing of established lesions (except for post-inflammatory hyperpigmentation or erythema from resolving lesions).
Complete remission on minimal therapy (CRmin)	The absence of new and established lesions completely healed while the participant is receiving prednisone therapy at $\leq 10$ mg/day for at least 2 months (8 weeks).
Complete remission off therapy (CRoff)	The absence of new and established lesions completely healed while the participant is receiving no prednisone therapy for at least 2 months (8 weeks).
Disease control (DC)	The absence of new lesions and the start of healing of established lesions.
Disease progression	Increase of $\geq$ 5 points in the PDAI activity score, observed at any post-baseline visit before DC.
Display	Analysis table, listing or figure
End of consolidation (EoC)	The time at which no new lesions have developed for a minimum of 2 weeks and approximately 80% of lesions have healed.
Flare	The appearance of 3 or more new lesions in a 4-week period that do not heal spontaneously within 1 week or the extension of established lesions, in a participant who had achieved DC.
Phase	Interval of time in the planned conduct of a study that is associated with a specific purpose: for example, screening, treatment, follow-up.

SGS	Statistical Analysis Plan		
ARGX-113-1905	Final analysis	Final 1.0 of 26APR2024	
Significant digit	All digits of a number used to express it to the required degree of accuracy, starting from the first non-zero digit.		
Standardized unit	unit populating –STRESU in the clinical database		
Study drug or investigational medicinal product (IMP)	Pharmaceutical form of an active ingredient or placebo, being tested or used as a reference in a clinical study.		
Treatment-emergent abnormality / toxicity	Any post-baseline abnormality/toxicity that was not present at baseline (e.g. hemoglobin normal or missing at baseline and grade 1 post-baseline; glucose low at baseline and high post-baseline; QTcF ]450; 480] ms at baseline and >500 ms post-baseline)		

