#### 2.2.4 Analysis visits

All assessments (except safety assessments in the roll-over phase), including unscheduled assessments, will be allocated to analysis windows. Tables, listings and figures will present the analysis windows as defined below, not the CRF visits.

Allocation of assessments will be done using their relative day in the phase (ADYP) (see section 2.2.3) according to the following table:

Phase	Analysis window	Target ADYP	Lower limit ADYP	Upper limit ADYP
Roll-Over	Baseline a	-	-	-
	Week 4	29	1 [c]	43
	Week 8	57	44	71
	Week $(8 + x^{b} * 4)$	$57 + (x^{b*28})$	$44 + (x^{b*28})$	$71 + (x^{b*28})$
	Week 52	365	352	End day of phase
Treatment	Baseline a	-	-	-
	Week 1	8	1°	11
	Week 2	15	12	18
	Week 3	22	19	25
	Week $(3+x^b)$	$22 + (x^{b*7} \text{ days})$	$19 + (x^{b*7} \text{ days})$	$25 + (x^{b*7} days)$

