#### Table 3: Analysis visits

Document template OTH.STAT.010 v3

Page 21 of 84

System Version: 1.0, Status: Approved, Document ID: VV-TMF-172580

SGS Statistical Analysis Plan				
ARGX-113-1905		Final	analysis	Final 1.0 of 26APR2024
	Week 51	358	355	361
	Week 52	365	362	End day of phase
Follow-up	FU Week 4	28	1	42
	FU Week 8	56	43	End day of phase

a Baseline is the assessment at the roll-over visit, so no analysis visit windows are required for this time point. For participants with a roll-over phase, the baseline analysis visit will be assigned to the roll-over phase and will not be repeated in the treatment phase. For participants without a roll-over phase, the baseline analysis visit will be assigned to the treatment phase.

b x=1,..., 10 for roll-over phase, x=1,...,.47 for treatment phase

An assessment at the roll-over visit will be attributed to Baseline in case it is before the first IMP administration, to Week 1 otherwise.

Baseline is defined in section 2.2.2.

For the analysis of ECG, a 12-weekly allocation will be used, as defined in Table 4.

Phase	Analysis window	Target ADYP	Lower limit ADYP	Upper limit ADYP
Treatment	Baseline a	-	-	-
	Week 12	85	1 a	127
	Week 24	169	128	211
	Week 36	253	212	295
	Week 48	337	296	361
	Week 52	365	362	End day of phase
Follow-up	FU Week 4	28	1	42
	FU Week 8	56	43	End day of phase

Table 4: Analysis visits for ECG

a Baseline is the assessment at the roll-over visit, so no analysis visit windows are required for this time point.

x=1 through the maximum number of 12-weeks periods on treatment for any participant minus 2

For GTI wider windows are used:

- Week 26 (wide range): from ADY=145 until ADY=221 with target on ADY=183
- Week 52 (wide range): from ADY=327 until ADY= end of treatment phase with target on ADY=365
- Other assessments will be allocated as in table 3 but will not be presented in the tables (only in listings).
- Additional visit window: Endpoint: last record post baseline.

_	SGS	Statistical Analysis Plan	
AF	GX-113-1905	Final analysis	Final 1.0 of 26APR2024

Analysis of ABQOL and EQ-5D-5L will be done on following visits:

- Roll-over (per CRF visit)
- At CRmin (assessment done within 28 days after achieving CRmin)
- At start of new treatment period
- At EoT/ET (per CRF visit)

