## 2.4.3 Ordering in tables, listings and figures

All tables and figures will be presented per treatment and total, unless specified otherwise. In by visit displays, worst-case will be shown last, if present.

In listings for general characteristics, results will be ordered by treatment and participant, unless specified otherwise.

All other listings will be ordered by treatment, participant, analysis visit and time point, unless specified otherwise.

Safety assessments during the roll-over phase will not be tabulated, unless specified otherwise. These assessments will be included in listings, ordered by treatment, participant and time point.

In tables showing several parameters, each parameter will begin on a new page and parameters will be sorted alphabetically, within the parameter category if applicable.

Treatment columns will be ordered in the same order as mentioned in section 2.4.2.

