#### 5.2.3 Presentation of results

The statistical analysis will present results in standardized units, except for eGFR, which will be reported in mL/min/ $1.73m^2$ .

Continuous laboratory parameters will be summarized by means of descriptive statistics of the actual values and changes from baseline at each analysis visit. For albumin and LDL-C, also percent changes from baseline will be shown. Categorical parameters will be listed only.

Laboratory abnormalities will be presented as cross-tabulations of the abnormality at each post-baseline analysis visit and at the worst-case analysis visit versus the baseline abnormality. This table will also show numbers of participants with treatment-emergent abnormalities (see Definition of terms). The denominator for the percentage is the total number of participants per treatment and per analysis visit in

SGS	Statistical Analysis Plan	
ARGX-113-1905	Final analysis	Final 1.0 of 26APR2024

the Safety analysis set. Abnormalities will not be tabulated for those parameters for which toxicity grades are defined.

Laboratory toxicity grades will be presented as cross-tabulations of the toxicity at each post-baseline analysis visit and at the worst-case analysis visit versus the baseline toxicity. This table will also show numbers and cumulative numbers over decreasing toxicity grading of participants with treatment-emergent toxicities. The denominator for the percentage is the total number of participants per treatment and per analysis visit in the Safety analysis set. Parameters having toxicity grades defined in both directions (hypo and hyper) will be shown by direction.

Tables to be produced for the topline results (see list of outputs in section 8.1) will show data for PV+PF participants as well as for PV participants.

All laboratory data will be listed, but only for participants with any post-baseline abnormality/toxicity or clinically significant value.

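### For participants who enter in CRmin or CRoff, safety shifts are measured from a roll-over value up to 48 weeks older than the first dose, so abnormalities already present before dosing are tabulated as treatment-emergent

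*SAP*

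**What the plan says.** SAP 2.2.3 sets one baseline for all safety parameters: "The baseline value for 1905 will be the value at the Roll-over visit". Protocol 9.5.1 says the same. For participants who have a roll-over phase, note a to SAP Table 3 adds that "the baseline analysis visit will be assigned to the roll-over phase and will not be repeated in the treatment phase".

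The SAP's Definition of terms makes a laboratory, vital-sign or ECG finding treatment-emergent by reference to that baseline, not to dosing: "Any post-baseline abnormality/toxicity that was not present at baseline". The counts appear in the cross-tabulations of SAP 5.2.3, 5.3.3 and 5.4.3. The worst case (2.2.5) is taken over the treatment and follow-up phases only.

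Safety data from the roll-over phase get no window: "All assessments (except safety assessments in the roll-over phase), including unscheduled assessments, will be allocated to analysis windows". They also get no table: "Safety assessments during the roll-over phase will not be tabulated, unless specified otherwise". Per SAP Table 1 that phase ends one minute before the first 1905 dose.

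Two other parts of the SAP work differently. For adverse events, "AEs starting during the roll-over phase will also be considered as post-TEAEs". For a few parameters a pre-dose reference exists: "Furthermore, for PDAI, PD, albumin and LDL-C a treatment period-specific baseline (TPnB) will be defined". Among safety parameters that covers only albumin and LDL-C, and only for descriptive changes.

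**The concern.** Participants who enter in CRmin or CRoff and are not in flare are observed without study drug and dosed only after a flare in 1905. For those who are dosed, the reference value can be most of a year old.

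- **False flags.** An abnormality that develops off drug and persists past the first dose is tabulated as treatment-emergent.
- **Missed flags.** An abnormality present at roll-over that resolves off drug and returns in the same category after dosing is not flagged. A return in a worse grade or the opposite direction is flagged.
- **Opposite classification.** An adverse event starting in the roll-over phase is a post-TEAE, while the matching laboratory abnormality, if it persists, is treatment-emergent.
- **No way to see it in the tables.** Protocol 9.5.5 plans safety analysis by status at entry. The adverse-event overview and main adverse-event tables in SAP 8.1 have that split, but the laboratory, vital-sign and ECG tables do not.

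These evaluations are part of the primary endpoint, and the primary objective names retreatment. For placebo-arm participants who enter in CRmin, the post-flare dose is also their first efgartigimod.

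**Working it through.** **Age of the baseline at first dose.** A new treatment cycle may start up to week 49 (protocol 4.1, SAP 1.2), and the last planned dose is at week 52. Weekly doses from week 49 to week 52 number 52 − 49 + 1 = 4, which reproduces the documents' stated minimum of 4 weeks of treatment. Protocol Table 1 places EoT at V1 + 51 weeks, so V1 is week 1 and the maximum gap is 49 − 1 = 48 weeks (336 days). If V1 is week 0, as in SAP Table 3 where week 1 has target day 8, the gap is 49 weeks (343 days). For starts up to week 44, the last week in which initiation is not optional, the gap is 43 or 44 weeks.

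**Data available in the gap.** Laboratory and vital-sign visits are four-weekly, so up to 48 / 4 = 12 of them (V1 + 4 to V1 + 48) are listed but not tabulated. ECGs off drug are taken only at baseline and EoS (protocol Table 1, note g). The ECG at start of retreatment (protocol Table 2, note h), done pre-dose, is therefore normally the only later reference.

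**Size of the misclassification.** The documents give neither abnormality rates nor the number affected, so the inputs here are assumptions. Each parameter is a stationary Gaussian value, abnormal above its (1 − prevalence) quantile, with correlation ρ over 4 weeks, hence ρ^(gap/4) over the gap, and no drug effect. With a 24-week gap the correlation between roll-over and pre-dose values is 0.90^6 = 0.53 or 0.95^6 = 0.74. The worst case is taken over four-weekly post-dose visits. There were 1,000,000 simulated participants per row, with prevalence 10% and a 24-week gap:

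| ρ | Post-dose visits | A: flagged vs roll-over | B: flagged vs pre-dose | C: flagged vs roll-over, already abnormal pre-dose | D: recurrence missed | A − B | C / A |
|---|---|---|---|---|---|---|---|
| 0.90 | 3 | 11.6% | 7.8% | 5.0% | 1.2% | 3.8 | 43% |
| 0.90 | 7 | 18.7% | 15.3% | 5.4% | 2.0% | 3.4 | 29% |
| 0.95 | 3 | 8.4% | 5.4% | 4.1% | 1.1% | 3.0 | 48% |
| 0.95 | 7 | 13.0% | 10.3% | 4.3% | 1.6% | 2.7 | 33% |

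C / A uses unrounded counts. As a check, A − B must equal C − D; in the first row 11.6 − 7.8 = 3.8 and 5.0 − 1.2 = 3.8.

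Other settings, approximately:

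| Setting | C | D | A − B (points) |
|---|---|---|---|
| Prevalence 5 to 20%, 24-week gap | 2.3–9.5% | 0.5–4.4% | 1.6–6.1 |
| Prevalence 10%, 8-week gap | 2.4–3.3% | 1.0–1.8% | 1.2–1.9 |
| Prevalence 10%, 44-week gap, 1 or 3 visits | 4.7–6.0% | 0.5–1.1% | 4.3–4.9 |

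Protocol Table 2 note l samples the laboratory weekly to retreatment + 8 weeks and then four-weekly. With that schedule continued to 28 or 36 weeks (prevalence 10%, 24-week gap), C is 4.8 to 6.2%, C / A is 26 to 34%, and A − B is about 3 to 4 points.

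**The case against.** The strongest reply is that this is a pre-specified choice. The SAP follows protocol 9.5.1, the study tests no hypothesis, and roll-over is a common remission-state reference. A pre-dose value taken at a flare may itself be flare-affected, and prednisone is restarted or changed at the same time, so neither baseline isolates the drug. This stands as a reason to keep the roll-over display. It does not make an abnormality present before dosing treatment-emergent.

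Clinically significant abnormalities are reported as adverse events, whose treatment-emergence is tied to dosing, and participants with a post-baseline abnormality have their data listed, including roll-over-phase values. TEAE counts are indeed unaffected and a reader can trace individual cases, but the tables remain wrong.

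SAP 2.2.1 sends assessments whose missing date or time prevents allocation to the treatment phase by default, so some pre-dose values might be tabulated as post-baseline. SAP 2.2.3 largely answers this by treating untimed day-1 assessments planned pre-dose as pre-dose.

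The affected group is limited to entrants who flare and are dosed, and 48 weeks is the maximum gap, not the typical one. The simulation is illustrative: under weekly sampling, a pre-dose baseline would still flag about 11 to 20% with no drug effect. The fix removes one identifiable error, not all null flags. The missing split by entry status is a separate matter that the fix does not address.

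**Conclusion.** The concern holds. For participants dosed after a drug-free roll-over phase, the safety tables measure change and emergence from a value up to 48 weeks before the first dose (49 under the other week convention), and they can contradict the adverse-event tables. This follows from the text and needs no assumption.

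The size does depend on assumptions. At 10% prevalence and a 24-week gap, about 4 to 6% of affected participants per parameter would be flagged although already abnormal before dosing, across both sampling schedules. The net excess over a pre-dose baseline is about 3 to 4 points, and 1 to 2% have an unflagged recurrence under four-weekly sampling. The number of participants affected cannot be derived from the documents. Anyone dosed at roll-over is unaffected for the first period. The change should be made, but it does not threaten the TEAE results.

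**What to change.** In SAP 2.2.3, for laboratory, vital-sign and ECG summaries of the treatment and follow-up phases, define baseline as the last non-missing value before the first 1905 dose. Apply it to changes from baseline, cross-tabulations, treatment-emergent flags and QTc change categories. For ECG in CRmin and CRoff entrants this means the pre-dose ECG at start of retreatment. State that the existing day-1 pre-dose rule covers these parameters, and amend note a to Table 3 to match.

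Keep the roll-over baseline as a labelled secondary display. Record the change in SAP 6.1 as a departure from protocol 9.5.1; protocol 9.1.1 allows minor changes of method to be documented this way. Optionally, extend the descriptive changes from treatment-period baseline to the remaining safety parameters. Per-period flags are not needed.

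The cost is SAP wording, one extra baseline flag in the datasets and some additional tables. No new data are required: laboratory and vital-sign values are collected four-weekly in the roll-over phase, and laboratory, vital-sign and ECG assessments are scheduled pre-dose at start of retreatment. The downside is two baselines to label and explain, with the caveat that a shift from the pre-dose value still does not separate study drug from the concurrent prednisone change.

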- ^o PK and PD (total IgG and IgG subtypes) samples will be taken every 4 weeks, at CR, and as of CR again every 4 weeks at on-site visits, as long as the participant is receiving efgartigimod PH20 SC treatment (until CRmin or the next on-site visit if CRmin is achieved during a week without an on-site visit), and 4 weeks after CRmin (or the next on-site visit) or EoT. Blood will be taken predose (within 2 hours before the start of IMP administration during visits when IMP is administered).
- ^p Blood will be taken for PK assessment predose (within 2 hours before the start of IMP administration during visits when IMP is administered). At UNS visits, blood samples for PK analysis will be taken only if IMP is administered.
- ^q Blood will be taken to test for immunogenicity to efgartigimod in serum and to rHuPH20 in plasma every 4 weeks, at CR, and as of CR every 4 weeks at onsite visits while the participant is receiving efgartigimod PH20 SC treatment (until CRmin or the next on-site visit if CRmin is achieved during a week without an on-site visit), and 4 and 8 weeks after CRmin (or the next 2 on-site visits) or EoT. NAb will be tested for all confirmed positive immunogenicity samples.
- ^r Blood will be taken every 4 weeks and at the visit when CR is observed for IgG autoantibody subtypes and specificity. Once CR is achieved, samples will be taken every 4 weeks at on-site visits until EoS.
- ^s The ABQOL and EQ-5D-5L will be administered at the start of retreatment, when achieving CRmin (or at the next on-site visit if CRmin is achieved during a week without an on-site visit), and at EoT/W52 only.
- ^t Questionnaires are to be completed before any other assessment.
- ^u Disease assessment parameters include DC, EoC, CR, CRmin, CRoff, flare, and treatment failure. Participants who have achieved CR and have new lesions should come to the clinic for a UNS visit for disease assessment.
- ^v Pictures of different anatomical regions may be taken per judgment of the investigator. As a guidance, time points of baseline, DC, CR and flare are indicated. Pictures may also be taken at intermediate time points.
- ^w Samples for lymphocyte populations will be taken at selected sites only: optionally at on-site visits at W13 (±2 weeks), W26 (±2 weeks), W39 (±2 weeks), W52 (±2 weeks) or EoT/ET and EoS, and mandatory at on-site visits at W52 (±2 weeks) or EoT/ET and EoS for participants in CRmin or CRoff.

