At blinded rollover from ARGX-113-1904 into ARGX-113-1905 participants may be in different clinical stages. Participants may have achieved CRmin, participants may have achieved CR without meeting the minimal therapy criterion, participants may have achieved DC or EoC (the time at which no new lesions have developed for a minimum of 2 weeks and approximately 80% of lesions have healed) without having achieved CR, participants may have had treatment failure or a flare after having achieved CRmin.

ARGX-113-1905 evaluates the ability to (further) taper prednisone therapy and achieve CRoff, the ability to achieve CR and CRmin for participants who had not yet achieved CRmin, and the

ability to treat flare; and assesses patient outcome measures and the safety, PD, PK, and immunogenicity of efgartigimod PH20 SC over the duration of the trial. Duration of CR, time to CRoff and the effects of retreatment by the study drug will be specifically evaluated during the trial.

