14.2.1.3.4	Cumulative Prednisone Dose: Descriptive Statistics by Disease Status at Roll-over	ROLL	TL
14.2.1.4.1	Proportion of Participants Who Experienced Flare After CRmin	ROLL	TL
14.2.1.4.2	Proportion of Participants Who Experienced Flare After CRmin by Disease Status at Roll-over	ROLL	TL
14.2.1.4.3	Time to Flare After CRmin: Descriptive Statistics	ROLL	TL
14.2.1.4.4	Time to Flare After CRmin: Descriptive Statistics by Disease Status at Roll-over	ROLL	TL
14.2.1.5.1	Number of Flares – Descriptive Statistics	ROLL	TL
14.2.1.5.2	Number of Flares – Descriptive Statistics by Disease Status at Roll- over	ROLL	TL
14.2.1.6.1	Proportion of Treatment Failures	ROLL	TL
14.2.1.6.2	Proportion of Treatment Failures by Disease Status at Roll-over	ROLL	TL
14.2.1.7.1	PDAI in PV Participants: Descriptive Statistics of Actual Values, Changes from Baseline, Changes from 1904 Baseline and Changes from Treatment Period Baseline by Visit	ROLL	
14.2.1.7.2	PDAI in PV Participants: Descriptive Statistics of Actual Values, Percent Changes from Baseline, Percent Changes from 1904 Baseline and Percent Changes from Treatment Period Baseline by Visit	ROLL	
14.2.1.7.3	PDAI in PV+PF Participants: Descriptive Statistics of Actual Values, Changes from Baseline, Changes from 1904 Baseline and Changes from Treatment Period Baseline by Visit	ROLL	TL
14.2.1.7.4	PDAI in PV+PF Participants: Descriptive Statistics of Actual Values, Percent Changes from Baseline, Percent Changes from 1904 Baseline and Percent Changes from Treatment Period Baseline by Visit	ROLL	
14.2.1.8.1	C-GTI: Descriptive Statistics of CWS and AIS at Week 26, Week 52 and Overall	ROLL	
14.2.1.9.1	ABQOL: Frequency Tabulation of 17 Items by Visit	ROLL	
14.2.1.9.2	ABQOL: Descriptive Statistics of Actual Values and Changes from Baseline in ABQOL Total Score by Visit	ROLL	
14.2.1.10.1	EQ-5D-5L: Frequency Tabulation of 5 Dimensions by Visit	ROLL	
14.2.1.10.2	EQ-5D-5L: Descriptive Statistics of Actual Values and Changes from Baseline in VAS Score by Visit	ROLL	
PHARMAC	OKINETICS		
14.2.2.1	Descriptive Statistics of Efgartigimod Serum Concentration over time	SAF	
D	Page 61 of 84		

•	SGS	Statistical Analysis Plan	
	ARGX-113-1905	Final analysis	Final 1.0 of 26APR2024

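### Quality-of-life change is taken only from roll-over, so for participants who entered in remission a retreatment course that restores quality of life shows a change of about zero

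*SAP*

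**What the plan says.** SAP 2.2.3 sets one general baseline: "The baseline value for 1905 will be the value at the Roll-over visit". It then makes an exception for some variables: "Furthermore, for PDAI, PD, albumin and LDL-C a treatment period-specific baseline (TPnB) will be defined", namely the last non-missing value before the first dose of that period. ABQOL and EQ-5D-5L are not among them.

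The table list in SAP 8.1 follows the same split. Table 14.2.1.9.2 is titled "ABQOL: Descriptive Statistics of Actual Values and Changes from Baseline in ABQOL Total Score by Visit" and table 14.2.1.10.2 "EQ-5D-5L: Descriptive Statistics of Actual Values and Changes from Baseline in VAS Score by Visit". The PDAI tables in the same list add change from the treatment-period baseline.

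SAP 2.2.4 gives the questionnaires four analysis visits: roll-over, a CRmin visit defined as "At CRmin (assessment done within 28 days after achieving CRmin", a visit labelled "At start of new treatment period", and end of treatment. The CRmin and new-period visits have neither a period number nor a target day. The overview in SAP 4.1.3.7 marks quality of life for the overall column only, not by disease status at roll-over.

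On collection, Protocol 1.3 (Table 2, footnote s) says "The ABQOL and EQ-5D-5L will be administered at the start of retreatment, when achieving CRmin", and again at week 52 or end of treatment. Protocol 4.2 adds that "the effects of retreatment by the study drug will be specifically evaluated during the trial".

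**The concern.** The questionnaire at the start of retreatment and the one at the next CRmin form a before-and-after pair for each retreatment course. The plan collects both but computes no difference between them. It measures each against roll-over instead. For someone who entered in remission, roll-over is a good-health value, so a return to remission after a flare gives a difference near zero, whatever the course achieved.

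The effect on quality of life is a secondary objective, and the protocol singles out retreatment for evaluation. A reader of the CRmin row would see a change that mixes two kinds of participant: those whose reference value was taken in active disease and those whose reference value was taken in remission. With no split by status at roll-over, the reader could not separate them.

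**Working it through.** The plan states no figure for this point, so there is none to reproduce. The ABQOL total runs from 0 to 17 x 3 = 51, and higher is worse (SAP 4.1.2.6). All scores, shares and counts below are assumptions.

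**Formulas (SAP 2.2.3).** Planned change = value at CRmin - roll-over value. Period change = value at CRmin - value before the first dose of period n.

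**One participant who entered in remission.** Let R be the remission score (at roll-over and at the new CRmin) and F the score at retreatment start.

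| R | F | Start-of-retreatment row, F - R | CRmin row, R - R | Period change, R - F |
|---|---|---|---|---|
| 0 | 15 | +15 | 0 | -15 |
| 5 | 20 | +15 | 0 | -15 |
| 5 | 25 | +20 | 0 | -20 |
| 10 | 30 | +20 | 0 | -20 |

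If recovery is not quite complete (8 at roll-over, 20 at flare, 9 at CRmin), the planned change is 9 - 8 = +1 and the period change is 9 - 20 = -11.

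**One participant who entered in flare.** Treatment starts at roll-over, so the roll-over value is F. The planned change is R - F, the same as the period change. Nothing is hidden.

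**Pooled CRmin row.** Assume a first-course change of -8, and let a share f of the CRmin records follow retreatment.
- Planned mean, if every retreated record comes from a remission entrant: -8(1 - f) + 1f, which is -6.2 at f = 0.2 and -4.4 at f = 0.4.
- Planned mean, if half of the retreated records come from participants who entered with active disease and still show -8: -8(1 - f) + f(1 - 8)/2, which is -7.1 and -6.2.
- Mean from period baselines, with -11 for every retreated course: -8(1 - f) - 11f, which is -8.6 and -9.2.

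**Can the two printed rows be subtracted instead?** Take R = 5 and F = 25. Suppose 40 participants entered with active disease and reached CRmin once. Another 20 entered in CRmin and were retreated, and 12 of them regained CRmin. The new-period row mean is +20.0. The CRmin row mean is (40 x -20 + 12 x 0)/52 = -15.4. The difference is -35.4, but the true paired change is -20. The rows hold different participants, so subtraction does not recover the pair.

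**Is CRmin after retreatment reachable?** From CR, the taper steps in Protocol 6.5.1 and Table 4 take 2 + 3 + 8 = 13 weeks from 20 mg, or 15 weeks from one step higher. If CR is assumed 2 to 8 weeks into the course, CRmin falls at week 15 to 23 of the period. A course begun by about week 29 to 37 can therefore reach it by week 52.

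**Two CRmin episodes in one participant.** SAP 2.2.4 keeps the value closest to the target day. The CRmin visit has no target day, so the rule cannot choose.

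**The case against.** The strongest reply is that no commitment is broken. Protocol 9.5.1 sets the 1905 baseline at the last 1904 visit, and Protocol 3 defines the quality-of-life endpoints as scores, not as change from a period baseline. The rule that retreatment starts a new baseline names DC, CR and the prednisone schedule, with an open-ended etc. The effects of retreatment are reported by period for CRmin, CRoff, the time-to-event endpoints, prednisone dose, flares, PDAI and PD. The study is descriptive and safety is primary. All of this stands, and it limits how serious the point is.

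Three stronger readings are tempting but are not supported:

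- A reader might infer that the retreatment questionnaires go unused. They do not: the start of a new period is a planned analysis visit, with actual values, change from roll-over and item frequencies (SAP 2.2.4, 4.1.3.6, 8.1). Only the paired change is missing.
- A reader might infer that every successful retreatment shows a change near zero. That holds only where the roll-over value was taken in remission.
- A reader might take the 28-day CRmin rule literally. It could then absorb a roll-over questionnaire completed soon after CRmin in 1904, or count a retreatment-start questionnaire as a remission value. SAP 2.2.4 makes roll-over a separate visit, so the first reading is strained. The second needs CRmin, a flare and retreatment all within 28 days, and that questionnaire has its own row. Nothing shows how often either would occur.

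The fix also has a limit. Participants who entered in CR but not CRmin begin period 1 in remission, so their period-1 change stays near zero with either baseline.

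**Conclusion.** The point holds for remission entrants who are retreated: the plan reports their quality-of-life change at the new CRmin as about zero, even where the course restored it. For the trial as a whole, no planned table gives the paired change over a retreatment course as a separate result. For participants who rolled over in flare, the change from roll-over is the course change, but it is pooled with everyone else's.

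The size is unknown, because the documents give neither ABQOL values nor the share of retreated participants who entered in remission. On the assumed scores, the individual contrast is +1 against -11. The diluted means of -6.2 and -4.4 are the worst case for those scores, since they assume that every retreated record comes from a remission entrant; at one half they become -7.1 and -6.2.

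The endpoints are descriptive, so no alpha or power is involved. The change is worth making because it is cheap and uses the method that the SAP already applies to PDAI.

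**What to change.** In SAP 2.2.3, add ABQOL total score and EQ-5D-5L VAS to the variables with a treatment-period baseline. State that for periods 2 and later this is the questionnaire at the start of retreatment. Questionnaires are sparse, and the general last-available rule could otherwise fall back on a remission value.

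In SAP 2.2.4, replace the two unnumbered visits by 'Start of treatment period n' and 'CRmin in treatment period n'. Define the latter as the first questionnaire on or after a CRmin reached in that 1905 period and before any flare. This also settles the case of two CRmin episodes and removes both literal readings of the 28-day rule.

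In tables 14.2.1.9.2 and 14.2.1.10.2, show change from the period baseline by period beside change from roll-over.

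The cost is SAP wording and some extra rows or columns in two tables. All the data are already collected. The downside is small numbers in periods 2 and later, which the SAP already accepts for PDAI and PD.
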